Family-centred care (FCC) is, in fact, developmentally supportive care that helps develop bonding (12). Intermittent kangaroo mother, as a part of FCC, benefits from maternal-neonatal bonding (13). Similarly, the role of maternal involvement in pre-feeding sensorimotor stimulation is a hidden corner in research. To our knowledge, not even a single international or national study is available in this regard.

In resource-constrained setups with limited properly trained speech therapists and neonatal nurses, mothers can be involved in pre-feeding sensory motor stimulation after training and teaching to improve their feeding performance. Within this context, the current study aims to determine the following: 1) the maternal role in sensory-motor stimulation for oral feed establishment in preterm neonates, 2) determine the effect of sensory-motor stimulation offered by the mother on the onset of oral feeding, and 3) the efficiency of mother-mediated stimulation techniques on oral feeding compared to trained nurses.

Keywords

Prematurity sensory-motor stimulation oral feed establishment, feeding intervention

Material and methods

An interventional, prospective, randomized control trial was conducted after ethical approval from the Institutional Review Board of Fatima Memorial Hospital (FMH-07-2021-IRB-929-M). The authors confirm that this intervention's ongoing and related trials are registered in the ClinicalTrials.gov platform—accession number NCT05484726. The study protocol can be accessed at <https://www.clinicaltrials.gov/ct2/show/NCT05484726>.

Study hypothesised that preterm babies who receive sensory motor stimulation from their mothers as compared to trained nurses, are

- Start taking oral feed at the same time as compared to the control group
- Take the same amount of milk at the commencement of oral feeding
- Take milk with equal efficiency
- Not face more adverse effects

The study period spans 16 months, from March 2022 to July 2023, in the department of Neonatology, Fatima Memorial Hospital, Lahore. We enrolled all preterm neonates of gestation age 28 to 34 weeks who were admitted to NICU during the study period after seeking consent from parents or guardians. All these neonates were haemodynamically stable, established gavage feed, had no respiratory distress, no need for respiratory support except LFNC and did not receive any kind of analgesics at time of enrollment.

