However, all those neonates having major anomalies incompatible with life, major malformations, syndromic babies, cleft lip and palate, genetic disorders, haemodynamically unstable babies including IVH (grade III & IV), haemodynamically significant PDA (HsPDA) requiring antifailure therapy, NEC (stage II & III) or anemia requiring blood transfusion. All those neonates with adverse events including cough with choking, breath holding, choking, aspiration, tachycardia HR > 200/min, bradycardia HR < 100/min, apnea > 15 sec, tachypnea RR > 70/min while stimulation or feeding were excluded.

Protocol

Interventional Study Model: Factorial Assignment

- Maternal involvement in perioral sensory-motor stimulation be in three stages
 - Observer status
 - Performing under supervision
 - Independent
- Intervention period: 5 days as
 - Training phase (T): T1 and T2 (for mothers by the nurse)
 - Direct feeding phase (D): F1, 2, and 3 (oral feed was offered to neonate)
- Stimulation for 7 minutes and 15 minutes before feeding twice a day at 1100 and 1700 hrs.
- Two groups
 - Intervention group (G I): by mothers
 - Control group (G II): by staff nurses

Number of Arms: 2

Masking: Single (Care Provider)

The mothers, medical staff involved in general care, nursing staff involved in the intervention, and doctors conducting the assessment of oral feeding skills (OFS) were all blinded to allocation. The nursing staff was informed at the time of intervention that participating infants received either sensory motor stimulation or sham oral stimulation depending on group allocation.

Allocation

Randomization was done using a random Alloc Software environment. Gestation age-based stratification was done using 3 blocks design of 28 to 30, 30+1 to 32 & 32+1 to 34. Random allocation of neonates into the intervention or control groups by stratum using lottery method.

Blinding

The mothers, medical staff involved in general care, nursing staff involved in intervention and doctors conducting the assessment of oral feeding skills (OFS) were all blinded to allocation. The nursing staff was informed at the time of intervention that participating infants received either sensory motor stimulation or sham oral stimulation depending on group allocation.

Sample size

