The sample size was 46 (23 each in interventional and control groups) and calculated with a 95% confidence level, 10% margin of error and 5% level of significance by taking feeding-related problems as 40%. It was done by using openepi.com.

Initially only 46 neonates were enrolled in study. But later an immense maternal response was observed. Mothers were ready to learn and involve in sensory motor stimulation of their neonates. Hence, the final total study population size was 97 with 49 in experimental and 48 in control group.

Procedure of intervention

- The study intermediation was started not before 30 weeks of postmenstrual age when full gavage feeding was established with the addition of supplements.
- All mothers in this study was involved in gavage feeding before involvement in the procedure.
- Trained nurses taught details of sensory-motor stimulation to mothers in easily understandable languages (annexure 1 in (a) English and (b) Urdu). This procedure has been adapted from modified from PIOMI and Fucile (14,15).
- Stimulation was done for 7 minutes and at least 15 minutes before feeding twice daily at 1100 and 1700 hrs till full oral feed establishment (expected time 28 days chronological age)
- Oral feeding was offered using a bottle with a slow-flow nipple.
- Time monitoring for feeding was strictly followed
- Infants was fed for a maximum of 20 min, and feeding was discontinued early if adverse events occur.

Arms and intervention

- Study groups for sensory motor stimulation (5 minutes) + pacifier (2 minutes)
 - Intervention group (G1) : by mothers
 - Control group (G 2) : by staff nurses

Experimental: Intervention group (Group 1)

- Maternal involvement was done in three stages for the intervention group as
 - Observer status
 - T1: Nurses performing all steps while mother observer status
 - T2: Nurses perform all steps in front of the mother and a pacifier was offered by the mother
 - Performing under supervision
 - D1: Mother performs all steps and oral milk was offered by the nurse while the mother observes.
 - D2: Mother performing all steps and offering oral milk while the nurse is supervising

- Independent
 - D3: Mother performing all steps independently
- Study groups for sensory motor stimulation
 - Assigned intervention perioral sensory motor stimulation Step 1 - 6 over 5 minutes + pacifier 2 minutes for total duration of 7 minutes.

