 - Step 1: With the help of the index finger, on the external surface of the cheek, make a circle starting from the angle of the mouth towards the ear then back 7x each cheek
 - Step 2: While holding both sides of the cheek with help of the thumb and index finger repeat step 1 7x each cheek
 - Step 3: Move index finger from one corner to opposite one over both lips separately 7x each lip
 - Step 4: Gentle massage and compress the gums from center to back of mouth 7x each half of the gum
 - Step 5: Move the finger from front to back on the hard palate while applying gentle pressure 7x
 - Step 6: Displace the center of the tongue with gentle pressure 7x
 - Offer pacifier at the end 2 minutes Note: 7x means 7 times

Control group / Sham Comparator (Group II)

All steps were same as intervention group and was performed by trained staff nurses

Data Collection

All relevant maternal and neonatal data (baseline measures) were collected on a specially designed proforma.

Baseline measures

- Maternal demographic and clinical data include
 - Age in years
 - Gravidity / number of pregnancies measured in numbers as primigravida (PG), 2-3 or ≥ 4)
 - Educational qualification as uneducated, primary, secondary or higher
 - Previous preterm baby measured as yes or no
 - Job status as working-lady or home-maker
 - Diabetes mellitus, hypertensive disorders and anemia as yes or no
- Neonatal demographic data includes
 - Gender as male or female
 - Gestation age measured in weeks
 - Mode of delivery as spontaneous vaginal delivery (SVD) or low segment caesarian section (LSCS)
 - Birth weight measured in kg
 - Weight for gestation age. It can be appropriate for gestation age (AGA), small for gestation age (SGA) or large for gestation age (LGA)
 - Place of birth as inborn or out-born
 - Neonates with respiratory failure may need respiratory support that was measured as
 - Requirement of invasive mechanical ventilation (IMV) along with duration in days as median with IQR

- Non invasive ventilation (NIV) along with duration in days as median with IQR
- Oxygen as low flow nasal cannula (LFNC) along with duration in days as median with IQR
- Neonates with prophylactic caffeine therapy given to all neonates < 32 weeks of gestation age
- Respiratory distress syndrome (RDS) was diagnosed on clinical and radiological features of reticulo-nodular shadowing
- Apnea was diagnosed on basis of breath holding spells for > 20 second

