- Hemodynamically significant patent ductus arteriosus (HsPDA) diagnosed by echocardiography
- Necrotizing enterocolitis (NEC) diagnosed using modified Bell's scoring (stage 1)
- Feeding intolerance diagnosed as aspirates > 20% of previous feed ± abdominal distension of > 2cm from base line
- Sepsis (leukocytosis or leukopenia or ANC<150 along with raised CRP and platelets <100 and or positive blood culture)
- Seizures
- Discharge weight in kg
- Duration of stay in NICU in days
- Neonatal feeding characteristics at time of enrollment in study include
 - Postmenstrual age (PMA) measured in weeks
 - Chronological age (ChA) measured in weeks
 - Time/duration to achieve full gavage/tube feed measured in days
 - Daily milk intake (ml/kg/day) when sensory motor stimulation was started
 - Volume of feed prescribed for each feed (ml)

The **outcome** measured were documented daily twice a day (11.00 and 17.00 hrs) until achievement of full oral feed. Full oral feed was volume of 120-140ml/kg/day taken orally. However, to make calculations concise, for both groups, all outcome parameters were documented on proforma for fixed time (11.00 am) for D1, D2, D3, D5, D7 and D14.

- Primary Outcome Measure
 - Transition time to full oral feeding is the time interval between commencement of perioral sensory stimulation on D1 to establishment of full oral feed in both groups. It was done daily till 14th day of perioral sensory motor stimulation. Transition time to full oral feeding was the day at which baby was able to take oral feed of volume of 120-140ml/kg/day.
 - Improvement (change) in efficiency oral feed establishment in terms of amount and time. It was classified into four levels depending upon the level of maturity in ascending order as follows:
 - Level 1: PRO < 30% and RT < 1.5 ml/min
 - Level 2: PRO < 30% and RT ≥ 1.5 ml/min
 - Level 3: PRO ≥ 30% and RT < 1.5 ml/min
 - Level 4: PRO ≥ 30% and RT ≥ 1.5 ml/min

For our RCT, efficacy was measured as the achievement of L4 for the intervention group vs the control group.

- Adverse outcome monitoring was done for every neonate from first day of enrollment in study (D1) till establishment of full oral feed (by D14 expected). These include non-life threatening adverse events including cough, tachycardia HR 180-200/min, bradycardia HR120 - 100/min, , tachypnea RR 60 - 70/min while maintaining SpO2 of >90% at room air
- Secondary Outcome Measure:
 - Total volume (TV) taken during each feed

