 - Volume taken during the first 5 min (TV₅) out of total feed taken orally
 - Rate of transfer (RT) ml/min i.e., how long it neonate takes to finish oral feed.
 - Overall transfer (OT percent) volume taken/total volume prescribed. It shows trend towards oral feed establishment.
 - Proficiency (PRO percent) volume taken during the first 5 min/total volume prescribed.
 - SSB (Suck Swallow Breaths) coordination coordinated, developed pattern of suck swallow and breathe. It is a subjective assessment.

Statistical analysis

The statistical software IBM SPSS Statistics version 21 (SPSS, Chicago, IL) was used for the statistical analysis of the data. Appropriate bivariate analysis was performed to identify the unadjusted differences between the cases and controls. Categorical variables were expressed as frequencies and percentages. According to Shapiro Wilk test all continuous variables were asymmetrically distributed. Mann–Whitney U test was used for nonparametric continuous variables and were described as medians and inter quartile range (IQR). Fisher exact/Chi square test was used to compare categorical variables. Mann-Whitney test was used to compare continuous variables. The p-value of < 0.05 was taken as statistically significant.

Results

During the research period, 1009 newborns were admitted to the Neonatal Intensive Care Unit (NICU). Among them, 142 were born prematurely, with gestational ages falling between 28 and 34 weeks. Out of the preterm neonates, a total of 130 were eligible for the study, as 12 had to be excluded for various reasons. These exclusions included 2 cases where mothers experienced serious postnatal complications, 1 instance of parental refusal to participate, 1 case with incomplete data, and 8 cases that did not meet the inclusion criteria due to different reasons such as syndromic features, cleft lip and palate, suspected inborn error of metabolism (IEM), intraventricular hemorrhage (grade IV), and hemodynamically significant patent ductus arteriosus (HsPDA). Consequently, 130 neonates were included in the study and randomly assigned, with 65 in each group for intervention and control. Sensory motor stimulation (SMS) was administered to 107 of these neonates, and the study was completed with 97 neonates (as illustrated in Figure 1).

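### The adverse-event outcome stops where the exclusion list starts, so the mother-versus-nurse safety comparison does not cover choking, aspiration, apnea or the more extreme vital signs

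*Combined protocol and SAP*

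**What the plan says.** **Exclusion criteria (Material and methods).** Neonates are excluded for a list of events that includes choking, cough with choking, breath holding, aspiration and a heart rate above 200/min. The list ends: "bradycardia HR < 100/min, apnea > 15 sec, tachypnea RR > 70/min while stimulation or feeding were excluded". The text does not say whether this applies before or after randomisation.

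**Outcome (Primary Outcome Measure, adverse outcome monitoring).** Monitoring runs from D1 until full oral feeding. The events are described thus: "These include non-life threatening adverse events including cough, tachycardia HR 180-200/min, bradycardia HR120 - 100/min", followed by "tachypnea RR 60 - 70/min while maintaining SpO2 of >90% at room air". Results treats adverse events as one of the primary outcomes.

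**Recording.** For reporting, "all outcome parameters were documented on proforma for fixed time (11.00 am) for D1, D2, D3, D5, D7 and D14".

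**Feeding (Procedure of intervention).** A feed has a time limit, and "feeding was discontinued early if adverse events occur". This concerns ending a feed. It does not say whether the infant stays in the study or how the event is counted.

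**Hypothesis and result.** The fourth hypothesis is that infants stimulated by their mothers do "Not face more adverse effects" than those stimulated by nurses. Results reports that the arms did not differ significantly on adverse events. Neither statement is limited by severity.

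**Flow (Results).** 130 infants were randomised, 65 per arm. "Sensory motor stimulation (SMS) was administered to 107 of these neonates, and the study was completed with 97 neonates".

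**The concern.** The events that matter most when mothers carry out intraoral stimulation and offer feeds, independently from D3, are choking, aspiration, apnea and marked changes in heart rate or breathing. These are named as grounds for exclusion and are not named in the outcome. If the rules were followed as written, an infant with one of these events is excluded rather than counted, and the comparison rests on milder events alone. A reader of the hypothesis and of the Results sentence would take the finding to cover adverse events in general. At stake is whether the trial answers its own safety hypothesis.

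**Working it through.** **1. The two definitions side by side.**

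| Event | Adverse-event outcome | Exclusion list |
|---|---|---|
| Fast heart rate | 180 to 200/min | above 200/min |
| Slow heart rate | 120 to 100/min | below 100/min |
| Fast breathing | 60 to 70/min | above 70/min |
| Cough | cough | cough with choking |
| Choking, breath holding, aspiration | not named | named |
| Apnea in stimulation or feeding | not named | longer than 15 s |

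In the three numeric rows there is neither overlap nor gap: a value beyond the outcome band falls in the exclusion range. This step needs no assumption.

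**2. Reproducing Table 3.** The printed percentages are shares of all infants with an event that day (D1: 36/67 = 53.7%), not arm rates. With arm sizes of 49 and 48, and Fisher's exact test:

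| Day | Mothers | Nurses | Difference, points (Newcombe 95% CI) | Printed p | One-sided p | Two-sided p |
|---|---|---|---|---|---|---|
| D1 | 36/49 = 73.5% | 31/48 = 64.6% | +8.9 (-9.3 to +26.4) | 0.234 | 0.234 | 0.385 |
| D2 | 14/49 = 28.6% | 14/48 = 29.2% | -0.6 (-18.2 to +17.0) | 0.563 | 0.563 | 1.00 |
| D3 | 12/49 = 24.5% | 12/48 = 25.0% | -0.5 (-17.5 to +16.4) | 0.570 | 0.570 | 1.00 |
| D5 | 2/49 = 4.1% | 0/48 = 0% | +4.1 (-3.9 to +13.7) | 0.253 | 0.253 | 0.495 |

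The interval is d - √[(p1 - l1)² + (u2 - p2)²] to d + √[(u1 - p1)² + (p2 - l2)²], where l and u are the Wilson limits of each arm. For D1 the Wilson limits are 59.7% to 83.8% and 50.4% to 76.6%. In points, the lower limit is 8.9 - √(13.7² + 12.0²) = -9.3, and the upper limit is 8.9 + √(10.3² + 14.1²) = +26.4, up to rounding.

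The printed p-values are one-sided, in the direction observed; Statistical analysis does not state sidedness. No day is significant either way. The counts reproduce, but each is a single figure per day, not split by type of event.

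**3. Who is in the comparison.** Randomised 130; stimulated 107; analysed 97 (49 and 48).
- Lost before stimulation: 130 - 107 = 23.
- Lost after stimulation began: 107 - 97 = 10, or 10/107 = 9.3%.
- Total losses by arm: 65 - 49 = 16 with mothers and 65 - 48 = 17 with nurses.
- Share of randomised infants in Table 3: 97/130 = 74.6%.

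The readable text does not split the 10 later losses by arm or give their reasons.

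**4. Where else the exclusion-list events might appear.** The only by-arm apnea count is in Table 1 (18 and 20). It is a neonatal characteristic, not tied to stimulation or feeding. No readable table or passage of text gives the exclusion-list events by arm.

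**The case against.** **The limit is disclosed.** The outcome section says the events are non-life-threatening, and Results introduces its sentence as being about the primary outcomes. On that reading, adverse events there means the outcome as defined, and no wider claim of equal safety is made. This stands in part and lowers the weight of the point. It does not rescue the fourth hypothesis, which has no severity limit and which the defined outcome cannot answer for the exclusion-list events.

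**Both lists are open.** Each is introduced as examples, so other events may have been recorded. This stands. It means that low SpO2, for instance, cannot be called uncounted merely because neither list names it. The outcome is nevertheless held to non-life-threatening events, and its bands stop at the exclusion limits.

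**A reader might infer that infants with serious events were removed after randomisation, hiding a difference or biasing efficacy.** The documents do not support this. Stimulation is the study procedure, so later use of the clause is plausible, but its timing is not stated. The reasons for loss may be in the CONSORT figure, which is not shown. Assuming, with no support in the text, that all 10 later losses and no completer had such an event, the two-sided Fisher p is 1.00 for a 5:5 split (5/54 against 5/53), 0.100 for 8:2 and 0.002 for 10:0 (10/59 against 0/48). The 10:0 split would also require 16 - 10 = 6 losses before stimulation with mothers against 17 with nurses. These figures show only that the answer depends on unreported facts. They are not evidence of an effect.

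**A reader might also see a contradiction over apnea.** Baseline measures says "Apnea was diagnosed on basis of breath holding spells for > 20 second", while the exclusion uses 15 s. The first is a baseline diagnosis and the second an event during stimulation or feeding, so no contradiction is shown.

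**Conclusion.** The point holds as one of scope and should be fixed. As defined, the adverse-event comparison covers non-life-threatening events and does not cover those on the exclusion list, while the hypothesis and the Results sentence are worded without that limit. This rests on the text alone. Its numerical size cannot be given: the number of exclusion-list events per arm is unknown, and it is not established that any of the 10 infants lost after stimulation had one. The wide intervals in Table 3 are a separate matter of precision. D1, the largest gap, is a day on which the nurse still offered the milk in the mothers' arm.

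**What to change.** 1. State when the adverse-event clause of the exclusion criteria was applied, before or after randomisation, and how many infants in each arm it affected. This should record what was done; the documents do not allow a rule to be asserted after the event.
2. From existing records of all 130 randomised infants, report by arm the number with at least one exclusion-list event during stimulation or feeding, and the number with any adverse event, each with the 95% CI of the difference. Label this post hoc. Monitoring ran from D1 to full oral feeding, so the records may hold more than the six daily readings in Table 3.
3. If these events cannot be recovered, limit the adverse-event statement in Results, and the answer to the fourth hypothesis, to non-life-threatening events as defined, among the 97 completers.

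The exclusion criteria and the outcome definition must be reconciled on how an infant with an exclusion-list event is counted. No clinical threshold or bedside rule is proposed.

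The cost is a record check, one extra table and a few sentences, with no new patients or visits. Item 3 alone needs no new data. The records may be incomplete, and the safety result may look less favourable.

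### Mothers and intervention nurses are said to be blinded and the control is called a sham, but the arms differ only in who delivers the same stimulation; assessor blinding is asserted without a procedure

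*Combined protocol and SAP*

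**What the plan says.** Under Protocol, the design field reads "Masking: Single (Care Provider". The paragraph below it, repeated almost word for word under Blinding, gives a longer list: "The mothers, medical staff involved in general care, nursing staff involved in intervention", followed by the feeding-skill assessors, of whom it says "doctors conducting the assessment of oral feeding skills (OFS) were all blinded to allocation". Both paragraphs add that nursing staff were told, when the intervention was given, that "participating infants received either sensory motor stimulation or sham oral stimulation depending on group allocation".

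Arms and intervention defines the groups by the person delivering the procedure: "Intervention group (G1) : by mothers", against staff nurses in the control group. In Group 1 the mother observes during T1 and T2 (offering the pacifier on T2), performs the steps on D1 while a nurse offers the milk, and then "D2: Mother performing all steps and offering oral milk while the nurse is supervising". On D3 she works independently. The control section carries the words Sham Comparator in its heading, but its text is: "All steps were same as intervention group and was performed by trained staff nurses".

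**The concern.** Masking and the type of comparator are the first things a reader uses to judge risk of bias. As written, the document tells that reader that four parties were masked and that the control was a sham. If either statement is untrue, the results will be given credit they have not earned.

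This matters more than usual because the hypotheses are of sameness and the Results section concludes that the two groups' skills were comparable. That conclusion depends on even-handed feeding, observation and recording. Three items are open to someone who knows the arm:

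- suck-swallow-breathe coordination, which the outcome list itself calls subjective;
- observed adverse events such as cough, listed under the primary outcomes;
- the early ending of a feed when an adverse event occurs, which changes volume and time and, through them, transfer rate and Level 4 status.

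**Working it through.** No sample size, power or event count is involved, so there is no planned figure to reproduce. The check sets the masking statements (Protocol; Blinding) against the arm descriptions (Procedure of intervention; Arms and intervention; Control group) and the recording of outcomes (Data Collection), one party at a time.

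1. **Mothers.** Allocation is mother delivery or nurse delivery. A Group 1 mother is trained and then carries out the steps, so she knows her arm by doing so. A control mother is not the person delivering them. Blinding to allocation is not possible for Group 1 mothers, and nothing is described that would achieve it for control mothers.

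2. **Intervention nurses.** They teach and supervise the mother in Group 1 and perform the steps themselves in Group 2. The task reveals the arm, so blinding is not possible.

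3. **Sham.** A sham would replace the active steps with an inactive imitation. The control section gives the same steps as Group 1 and changes only the person. The control is therefore an active comparator. Table 3 analyses 49 experimental and 48 control infants, so the sham label is wrong for 48 of 48 analysed controls.

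4. **Masking field.** One masked party (care provider) is declared against four in the text. If care provider means whoever delivers the intervention, that is a party that cannot be masked (items 1 and 2). If it means general-care medical staff, the field does not say so, and it still omits the other three.

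5. **Feeding-skill assessors.** Stimulation ends at least 15 minutes before the feed, so an assessor need not see it. On D1 a nurse offers the milk in Group 1. On D2 the mother expressly offers it. On D3 she does everything independently, which probably includes the milk but may refer only to the numbered stimulation steps. For D5, D7 and D14 the feeder is not stated. The document does not say who feeds control infants, or whether assessors watch the feed or work from recorded volumes and times. If they watch, and if a nurse feeds controls, the arm can be inferred from D2. Neither condition is established.

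6. **General-care staff.** Whether they were at the cot at 11:00 or 17:00 is not stated. Their blinding is neither supported nor refuted.

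Result: of the four parties listed as blinded, two (mothers, intervention nurses) contradict the arm definitions and two (assessors, general-care staff) are asserted without a procedure.

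**The case against.** The best defence is that much of the outcome set rests on measurement. Time to full oral feeding is a volume threshold, Level 4 is a pair of cut-offs on proficiency and transfer rate, and most adverse-event definitions are heart-rate or respiratory-rate ranges. The one outcome called subjective is secondary. This stands in part: an assessor has less room for judgement on a measured volume than on coordination or cough. It does not dispose of the matter, because the person feeding can influence how much is taken and when the feed ends.

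Four stronger readings are tempting, and the document does not support them.

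- *Nobody could be blinded, so the whole trial was open-label.* This follows for mothers and intervention nurses only. An assessor working from recorded figures could have been kept unaware.
- *Assessors were compromised on five of the six tabulated days.* Only D2 expressly has the mother offering milk, and the count also needs assessors at the feed and nurses feeding the controls.
- *The text admits that nurses were told each infant's group.* The sentence can equally mean that they were told of the two possibilities. The nurses' lack of blinding follows from their role and does not need this sentence.
- *The sham label shows that the trial claims an effect of stimulation over none.* The hypotheses compare mothers with trained nurses, and the Results report only comparability. The label could mislead a reader, particularly beside the loosely worded second aim, but no such effect is reported.

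**Conclusion.** The document claims masking of mothers and intervention nurses, and a sham control, that its own design rules out. Its masking field also disagrees with its blinding paragraphs. These three points rest only on the arm definitions and need no assumption. They must be corrected, because they misdescribe two basic features of the trial.

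Blinding of assessors and general-care staff is unsupported, which is a weaker finding. For assessors it is doubtful from D2, on the assumption that they watched the feed and that control infants were not also fed by their mothers. It is not shown to be impossible.

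No direction or amount of bias is demonstrated, and a reader should not infer that the reported similarity is an artefact. What changes is the support for that similarity. It cannot lean on blinding of the people who delivered the intervention, and for coordination and observed adverse events it cannot lean on assessor blinding unless a procedure is documented.

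**What to change.** - In the masking field and both blinding paragraphs, state that mothers and intervention nurses were not blinded, and make the field agree with the text.
- Replace the sham wording throughout, including the control-arm heading and the sentence about what nurses were told, with active comparator (nurse-delivered stimulation).
- State whether and how assessors and general-care staff were kept unaware of the arm, who fed control infants, and who offered the milk in Group 1 after D2.
- Claim assessor blinding only for outcomes derived from recorded volumes and times by someone who did not see who delivered the stimulation or the feed. Otherwise report suck-swallow-breathe coordination and observed adverse events as not assured to be blinded.
- Qualify the conclusion of comparable skills accordingly, and note that the feeder's knowledge of the arm could also affect volumes and the early ending of feeds.

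The cost is wording in the protocol and the report, and in the registry entry if it carries the same statements. No data or analysis change. The downside is a less favourable risk-of-bias statement.
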